4.4.2 Dose Modification

For patients who do not tolerate the protocol-specified dosing schedule, adjustments in grapiprant and eribulin doses are permitted to allow the patient to continue the study treatment. All dose modifications must be based on the worst preceding toxicity as graded by the NCI-CTCAE version 5.0. Those will also be counted as DLT when it meets DLT definition. The DLT will be defined as any of the following be "probable," "possible," and "definite events occurring in the first 21 days (cycle 1):

- Any Grade 3 hematologic toxicity with the following changes: grade 3 platelet count (< 50,000/mm³–25,000/mm³) with associated bleeding (without bleeding, grade 4 platelet count [< 25,000/mm³] will be defined as DLT); grade 3 absolute neutrophil count (<1,000–500/mm³) that persists for 7 or more days despite of the use of the grown factor support or that is associated with fevers (febrile neutropenia). (Otherwise, grade 4 absolute neutrophil count [< 500/mm³] will be defined as DLT.)
- Hepatocellular injury is indicated by 3-fold or greater elevations above the ULN of ALT or AST in addition to the elevation of serum total bilirubin > 2 x baseline. In such cases, no other reason can be found to explain the combination of increased transaminases and total bilirubin such as viral hepatitis, preexisting or acute liver disease, or another drug capable of causing the observed injury (Hy's Law). For patients with liver metastasis, 6-fold or greater elevations above the baseline of ALT or AST in addition to the elevation of serum total bilirubin > 4 x baseline.
- All other grade 3+ electrolyte abnormality associated with clinical symptoms, regardless of duration.
- Grade 3 nausea or vomiting that does not improve to Grade 1 within 72 hours of initiating supportive therapy.
- Any other non-hematologic grade ≥ 3 toxicity deemed to be related to the study drug that lasts 72 hours or more will be considered a DLT.
- A grade \geq 3 laboratory abnormality that is determined to be of no clinical significance by the investigators will not necessarily constitute a DLT.
- Any death not clearly due to the underlying disease or extraneous causes.

Dose modification at the time of toxicities will be conducted as follows:

Product: Grapiprant
Protocol 2021-0077 Proprietary Information of MD Anderson
[name]
Product: Grapiprant

PI: [name] Co-PI: [name] Date: 11/22/2022

Grapiprant

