Safety management guidelines, including dose modification algorithms, are provided. Please note, in cases where the investigator is directed to permanently discontinue study treatment, these instructions are mandatory as described in this section. An overview of the available grapiprant dose modification guidelines is presented in **Table 1**. All AEs are to be graded according to NCI-CTCAE, version 5.0 (http://ctep.cancer.gov). All dose modifications and the reason(s) for the dose modification must be documented in the eCRF. The major classes of grapiprant toxicity described in **Table 2** include "Cardiac", "Blood pressure", and "Gastrointestinal", "Renal", and "Hepatic".

Investigators should refer to the grapiprant IB and Eribulin PI for additional information regarding the background of each drug and the management of other AEs or potential safety-related issues.

In case a dose reduction is necessary, the dose level or schedule of grapiprant may be changed as determined by the investigator and IKENA Oncology, consistent with the instructions for dose level and schedule (**Table 2**). If either study treatment is deemed intolerable and requires discontinuation despite optimal management, as described below, the participant must be discontinued from the study treatment, unless clinical benefit has been demonstrated. Any participant who requires a decrease in the grapiprant dose below 100 mg BID will discontinue grapiprant treatment and will come off study. Patients may continue to receive eribulin off study per standard of care if clinical benefit has been demonstrated per attending physicican discretion. Any participant that is required to discontinue eribulin for an AE may only continue on grapiprant if clinical benefit has been demonstrated and with agreement from the IKENA Oncology.

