	consider changing administration of grapiprant to 2 weeks on/ 1 week off
	• If symptoms continue or worsen to Grade 3-4, follow
C 1. 2. 4	algorithm for Grade 3-4 events
Grade 3-4	Interrupt or discontinue study treatment
	Consult sub-specialist
	Discuss with IKENA Oncology
	Follow-up:
	Symptoms improve to Grade ≤ 1 :
	Restart study treatment at a lower dose of grapiprant
	• If potentially related to cumulative toxicity (past first cycle),
	consider changing administration of grapiprant to 2 weeks
	on/ 1 week-off
	Symptoms ongoing:
	• Discuss further management with consultant and IKENA
	Oncology
	Consider alternative therapy
CAPDIAC	
CARDIAC	
Arrhythmia (tachycardia: supravent	ricular tachycardia, atrial fibrillation)
	First Occurrence:
	Omit grapiprant
	Perform a repeat ECG within 1 hour of the first occurrence.
	Seek cardiologist input; address electrolytes, calcium, and
	magnesium abnormalities; concomitant medication must be
	reviewed.
	Second Occurrence:
	Permanently discontinue patient from grapiprant
Other Cardiac Events	
Grade 1 or 2	Continue study treatment at same dose
Orauc I Or Z	Commue study deathent at same dose

Product: Grapiprant
Protocol 2021-0077 Proprietary Information of MD Anderson
PI: [name]

Co-PI: [name] Date: 11/22/2022

Grade 3	Omit dose until resolved to ≤ Grade 1, then decrease 1 dose	
Grade 3	level	
Grade 4	Permanently discontinue patient from grapiprant	
BLOOD PRESSURE		
Hypertension * true uncontrolled hy warrant a dose reduction	pertension, not present at baseline, judged by the investigator to	
Grade 1: systolic BP (sBP) 120-139 mmHg or diastolic BP (dBP) 80-89 mmHg	Continue study treatment at same dose	
Grade 2: sBP 140-159 mmHg or dBP 90-99mmHg	Omit dose until resolved to ≤ Grade 1 Perform an ECG and seek cardiologist input per physician discretion; address electrolytes, calcium, and magnesium abnormalities; review concomitant medication. Once hypertension was resolved, the grapiprant may be restarted by decreasing 1 dose level. Continue measuring blood pressure daily at home.	
Grade 3: sBP ≥ 160mmHg or dBP ≥ 100 mmHg	Omit grapiprant Perform an ECG and seek cardiologist input per physician discretion; address electrolytes, calcium, and magnesium abnormalities; review concomitant medication. Permanently discontinue patient from grapiprant	
GASTROINTESTINAL		
Colitis		
Grade 1	Continue study treatment at same dose	
Grade 2	Omit dose until resolved to ≤ Grade 1, then restart at the same dose.	

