We will administer eribulin with 1.4mg/m^2 on day 1 and day 8 in every cycle. We will assess eribulin's adverse reactions by obtaining the blood sample and physical examination, especially for peripheral neuropathy. We will not administer eribulin on day 1 or day 8 in patients with \geq grade 3 neutropenia, \geq grade 2 thrombocytopenia, or grade 3/4 nonhematologic toxicities. The day 8 dose may be delayed for up to 1 week in patients with toxicities. If toxicities resolve or improve to grade 2 or less by day 15, we will administer eribulin at a reduced dose and initiate the next cycle no sooner than 2 weeks later. If toxicities do not resolve or improve to grade 2 or less by day 15, we will omit the dose. If a dose has been delayed for toxicities that have recovered to the severity of grade 2 or less, resume the recommended reduced dose. If a dose has been reduced due to toxicities, we will not re-escalate.

Table 3. Recommended eribulin dose modifications and criteria for treatment interruption and re-initiation with treatment-related adverse events

DOSE MODIFICATIONS FOR ERIBULIN						
Toxicity (CTCAE 5.0 Eribulin Dose Modifications Grade)						
HEMATOLOGICAL						
Neutropenia (ANC)						
$ANC < 500/mm^3 \text{ for } > 7 \text{ days or}$						
$ANC < 1,000/mm^3$ with fever or	Hold eribulin until ANC is $\geq 1,000$ and platelet count is ≥ 75 x					
infection	10 ⁹ /L, then decrease 1 dose level permanently					

Protocol 2021-0077 Proprietary Information of MD Anderson PI: [name]

Co-PI: [name] Date: 11/22/2022

Any event requiring permanent dose reduction while receiving 1.1 mg/m ²	Hold eribulin until ANC is $\geq 1,000$ and no fever, then decrease 1 dose level
Any event requiring permanent dose reduction while receiving 0.7 mg/m ²	Discontinue eribulin
Anemia (Hemoglobin)	
Grade 1	Maintain dose level and continue eribulin with caution
Grade 2	Hold eribulin until hemoglobin is Grade 1.
Grade 3-4	Hold eribulin until hemoglobin is Grade 1, then decrease 1 dose level
Thrombocytopenia (Platelet)	
Platelets < 25,000/mm ³ or platelets < 50,000/mm ³ requiring transfusion	Hold eribulin until platelet (g/dL) is \geq 100,000, then decrease 1 dose level permanently
Any event requiring permanent dose reduction while receiving 1.1 mg/m ²	Hold eribulin until platelet (g/dL) is \geq 100,000, then decrease 1 dose level
Any event requiring permanent dose reduction while receiving 0.7 mg/m ²	Discontinue eribulin
NEUROLOGICAL	
Peripheral neuropathy	

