- Cycle 1 and 2: every other week (if visit schedule allows more frequent monitoring, this should be considered) or more frequently if clinically indicated, especially for patients with borderline acceptable AST/ ALT/ bilirubin* values
- Cycle 3 and onward: monthly or more frequently if clinically indicated

In case of any occurrence of ALT/AST/ bilirubin* increase \geq grade 2, LFTs must be monitored weekly or more frequently if clinically indicated until resolved to \leq grade 1.

In case of any occurrence of ALT/ AST/ bilirubin* increase \geq grade 3 LFTs must be monitored weekly or more frequently if clinically indicated until resolved to \leq grade 1; thereafter, the monitoring should be continued every other week or more frequently if clinically indicated. until the end of treatment with study medication

Patients who discontinued treatment with eribulin should be monitored weekly, including LFTs* or more frequently if clinically indicated until resolved to \leq grade 1 or stabilization (no CTCAE grade change over 4 weeks).

All other AEs	
Grade 1 or 2	Per physician discretion.
Grade 3	Omit dose until resolved to ≤ Grade 1, then decrease 1 dose level.
Grade 4	Permanently discontinue the patient from eribulin. Note: Omit dose for ≥ Grade 3 vomiting or Grade 3 nausea only if the vomiting or nausea cannot be controlled with optimal antiemetic treatment.

Protocol 2021-0077 Proprietary Information of MD Anderson PI: [name]

Co-PI: [name] Date: 11/22/2022

Dosing interruptions are permitted in the case of medical/surgical events or logistical reasons not related to study therapy (e.g., elective surgery, unrelated medical events, patient vacation, and/or holidays). Subjects should be placed back on study therapy within 3 weeks of the scheduled interruption. The reason for interruption should be documented in the patient's study record. Subjects who experience a recurrence of the same severe or life-threatening event at the same grade or greater with a re-challenge of grapiprant will be discontinued from trial treatment.

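### The 72-hour condition in the DLT definition covers grade 4 as well as grade 3, so a brief related grade 4 non-hematologic event in cycle 1 is usually not counted

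*Combined protocol and SAP*

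**What the plan says.** DLT is a primary outcome (section 4.1). It is defined in the Synopsis and again in section 4.4.2, for events in the first 21 days that are possibly, probably or definitely related.

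- **Catch-all.** Other non-hematologic events of grade 3 or higher count under one condition: "toxicity deemed to be related to the study drug that lasts 72 hours or more will be considered a DLT". Both lists carry it.
- **Hematologic bullet.** Grade 4 counts need no minimum duration: "Otherwise, grade 4 absolute neutrophil count" is a DLT as it stands, and so is a grade 4 platelet count.
- **Other bullets without the 72-hour condition.** These are combined transaminase and bilirubin elevation of the Hy's Law type, death, and symptomatic electrolyte abnormality of grade 3 or higher. The electrolyte bullet is in 4.4.2 but not in the Synopsis.
- **Nausea and vomiting.** The bullet names grade 3 only, so grade 4 vomiting falls to the catch-all.
- **Laboratory exception.** A grade 3 or higher "laboratory abnormality that is determined to be of no clinical significance by the investigators will not necessarily constitute a DLT".

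Table 2 in 4.4.2 sets grapiprant dosing for the individual patient. For grade 4 in the other-cardiac row it says "Permanently discontinue patient from grapiprant", with no duration condition, and the text above the table says that "in cases where the investigator is directed to permanently discontinue study treatment, these instructions are mandatory as described in this section". Section 4.4.2 also says that events behind dose modifications count as DLTs only when they meet the DLT definition.

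The phase Ib rule is in section 7.0. With 0 or 1 DLT in 6 patients, phase II starts at that dose. With 2 or more in the first 3, or 2 in 6, the dose goes from 300 mg to 200 mg BID, or the safety trial stops if this happens at 200 mg. The same toxicities are monitored during cycle 1 of phase II.

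**The concern.** A duration allowance is easy to justify for grade 3 events, many of which respond to supportive care. It is harder to justify for grade 4. For events outside CTCAE, the protocol's own general grading (section 5.3.1) describes grade 4 as life threatening. Under the catch-all, a related grade 4 cardiac event that resolves in six hours adds nothing to the DLT count, although Table 2 ends the experimental drug for that patient. A neutrophil count that is briefly below 500/mm³ does count.

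The decision turns on a single patient. If one of six patients has a counted DLT and another has a brief grade 4 cardiac event, the tally is 1/6 and the rule clears 300 mg. If the second event counted, 2/6 would mean de-escalation. Two brief grade 4 cardiac events with no other DLT would read 0/6.

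**Working it through.** **Step 1: which bullet catches a brief, related, non-fatal grade 4 non-hematologic event in cycle 1?**

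| Event | Counted? | Reason |
|---|---|---|
| Grade 4 ANC or platelets, any duration | Yes | Hematologic bullet |
| Hy's-Law-type liver injury | Yes | No duration condition |
| Symptomatic grade 4 electrolyte abnormality | Yes in 4.4.2; not by its own bullet in the Synopsis | Bullet absent from the Synopsis |
| Grade 4 event still at grade 3 or higher at 72 hours | Yes | Meets the catch-all |
| Any other grade 4 event below grade 3 within 72 hours | No | No bullet reaches it |

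Only the last row is affected (and, under the Synopsis list, brief symptomatic electrolyte events).

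**Step 2: how the dosing rules treat these events.** Only the grade 4 other-cardiac row is a clear mandatory stop of grapiprant for an event that can miss the DLT list. The general grade 3-4 row of Table 2 allows "Restart study treatment at a lower dose of grapiprant" after improvement, and a first arrhythmia leads only to omission of grapiprant. For eribulin the text is unsettled. The narrative says "If toxicities resolve or improve to grade 2 or less by day 15, we will administer eribulin at a reduced dose", while the grade 4 row for all other adverse events in Table 3 says "Permanently discontinue the patient from eribulin".

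**Step 3: size.** The plan states no operating characteristics for the phase Ib rule, so there is no figure to reproduce. The chance of clearing a dose at true DLT rate p is

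F(p) = (1−p)^6 + 6p(1−p)^5.

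The 3-then-3 path gives the same value, because 2 or more DLTs in the first 3 already means 2 or more in 6. At p = 10%: 53.14% + 35.43% = 88.57%.

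Let c be the DLT rate under the present definition, and u the share of patients whose only such event is a brief, uncounted grade 4 non-hematologic event. The effect of leaving these events out is F(c) − F(c+u). Both c and u are assumptions. The upper value, c = 29%, is a rough high one: section 6.2 reports grade 4 neutropenia in 29% (144/503) on eribulin alone, over all cycles and not cycle 1 only.

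| c | F(c) | u = 0.1% | u = 0.5% | u = 1% |
|---|---|---|---|---|
| 10% | 88.57% | 88.38% (0.20 points) | 87.58% (1.00) | 86.55% (2.02) |
| 20% | 65.54% | 65.29% (0.25) | 64.31% (1.23) | 63.08% (2.46) |
| 29% | 44.20% | 43.98% (0.22) | 43.10% (1.10) | 42.02% (2.19) |

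**Step 4: a rough ceiling for cardiac events.** Section 6.1 lists 9 potentially treatment-related cardiac events and describes none as grade 4. If they arose in the roughly 1000 people mentioned in section 3.3 (an assumption), cardiac events of any grade and duration are about 9/1000 = 0.9%. At u = 0.9% the effect is 1.81, 2.21 and 1.97 points for c = 10%, 20% and 29%. The brief grade 4 share must lie below that. No comparable figure exists for non-cardiac events.

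**The case against.** The best defence is that the two sets of rules have different jobs. Table 2 manages one patient's dosing, the DLT list decides the cohort dose, and section 4.4.2 keeps them apart. This stands. A reader might infer that the protocol contradicts itself, or that every mandated stop ought to be a DLT, and the text supports neither. Grade 3 hypertension and a second arrhythmia also end grapiprant, and nothing shows that the authors meant each such stop to count. What remains is the uneven treatment of grade 4: no duration test for blood counts, 72 hours for most other organ systems.

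It can also be said that the rule does not act alone.

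- Section 7.0 requires IND Office approval before dose levels are expanded or changed, so a 1/6 tally does not by itself release the dose. The approval is mandatory, but its outcome is a judgement.
- All SAEs go to the IND Office within 5 working days, and unexpected related deaths or life-threatening events within 24 hours (section 5.3.2.1).
- Section 4.8 allows termination for unacceptable risk.
- A grade 3/4 toxicity rate above 30% prompts review after 9 patients. Section 4.8 gives no duration condition for it, but section 7.0 ties the monitoring to the DLT toxicities, so whether brief events enter is arguable. Two events would not trigger it in any case (2/9 = 22%).

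These safeguards lower the risk. None changes the number that the 1/6 versus 2/6 rule reads.

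Finally, materiality is not shown. This is fair. Eligibility requires LVEF of at least 50% and excludes the listed cardiac diseases, which should make cardiac events rarer still. A reader might assume rates of several percent and infer a large effect, but the documents offer no basis for such rates.

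**Conclusion.** The point holds as an inconsistent ranking of severity with a cheap remedy. It is neither an arithmetic error nor a flaw of demonstrated material effect. On the wording of both lists, a related grade 4 non-hematologic event that falls below grade 3 within 72 hours is left out of a primary safety count that decides the dose, subject to the exceptions in Step 1. The same gap carries into phase II monitoring.

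The average effect is probably small: 0.20 to 0.25 points on the chance of clearing the dose at an assumed 0.1% event rate, 2.0 to 2.5 points at 1%, for assumed DLT rates of 10% to 29%. The reason to act is the uncommon cohort in which such an event would decide the dose.

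A reader might also infer that a patient stopped mid-cycle drops out of the denominator, because the reporting schedule in section 7.0 speaks of evaluable patients who complete a cycle. The decision rule in that section counts DLTs among the 3 or 6 patients and removes nobody, so no denominator change is proposed.

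**What to change.** In both DLT lists (Synopsis and 4.4.2), limit the 72-hour condition in the catch-all to grade 3, and add: *Any related grade 4 non-hematologic toxicity in cycle 1 is a DLT regardless of duration, except a laboratory abnormality judged not clinically significant.* The exception follows the laboratory bullet already there. The 72-hour allowance for grade 3 stays, and mandated stops below grade 4 are not added.

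The cost is one edited bullet and one sentence in two places, with no new data. The downside is a slightly higher chance of not clearing 300 mg, by the same amounts as in the table above (about 2.0 to 2.5 points per 1 percentage point of newly counted events). De-escalation leads to the 200 mg path, with 22 or 19 patients and a stated power of 86% or 82%.

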We will administer eribulin with 1.4mg/m^2 on day 1 and day 8 in every cycle. We will assess eribulin's adverse reactions by obtaining the blood sample and physical examination, especially for peripheral neuropathy. We will not administer eribulin on day 1 or day 8 in patients with \geq grade 3 neutropenia, \geq grade 2 thrombocytopenia, or grade 3/4 nonhematologic toxicities. The day 8 dose may be delayed for up to 1 week in patients with toxicities. If toxicities resolve or improve to grade 2 or less by day 15, we will administer eribulin at a reduced dose and initiate the next cycle no sooner than 2 weeks later. If toxicities do not resolve or improve to grade 2 or less by day 15, we will omit the dose. If a dose has been delayed for toxicities that have recovered to the severity of grade 2 or less, resume the recommended reduced dose. If a dose has been reduced due to toxicities, we will not re-escalate.

Table 3. Recommended eribulin dose modifications and criteria for treatment interruption and re-initiation with treatment-related adverse events

DOSE MODIFICATIONS FOR ERIBULIN						
Toxicity (CTCAE 5.0 Eribulin Dose Modifications Grade)						
HEMATOLOGICAL						
Neutropenia (ANC)						
$ANC < 500/mm^3 \text{ for } > 7 \text{ days or}$						
$ANC < 1,000/mm^3$ with fever or	Hold eribulin until ANC is $\geq 1,000$ and platelet count is ≥ 75 x					
infection	10 ⁹ /L, then decrease 1 dose level permanently					

Protocol 2021-0077 Proprietary Information of MD Anderson PI: [name]

Co-PI: [name] Date: 11/22/2022

Any event requiring permanent dose reduction while receiving 1.1 mg/m ²	Hold eribulin until ANC is $\geq 1,000$ and no fever, then decrease 1 dose level
Any event requiring permanent dose reduction while receiving 0.7 mg/m ²	Discontinue eribulin
Anemia (Hemoglobin)	
Grade 1	Maintain dose level and continue eribulin with caution
Grade 2	Hold eribulin until hemoglobin is Grade 1.
Grade 3-4	Hold eribulin until hemoglobin is Grade 1, then decrease 1 dose level
Thrombocytopenia (Platelet)	
Platelets < 25,000/mm ³ or platelets < 50,000/mm ³ requiring transfusion	Hold eribulin until platelet (g/dL) is \geq 100,000, then decrease 1 dose level permanently
Any event requiring permanent dose reduction while receiving 1.1 mg/m ²	Hold eribulin until platelet (g/dL) is \geq 100,000, then decrease 1 dose level
Any event requiring permanent dose reduction while receiving 0.7 mg/m ²	Discontinue eribulin
NEUROLOGICAL	
Peripheral neuropathy	
Grade 1	Maintain dose level.
Grade 2	Omit dose until resolved to ≤ Grade 1, then restart at the same dose.
Grade > 3	Omit dose until resolved to ≤ Grade 1, then decrease 1 dose level.
HEPATIC	
AST or ALT	
Grade 1 (> ULN-3.0 x ULN)	Maintain dose level with liver function tests (LFTs)** monitored per protocol
Grade 2 (> 3.0– 5.0 x ULN) without	Omit dose until resolved to \(\le \text{Grade 1, then} \)
total bilirubin elevation to > 2.0 x ULN	-If resolved in ≤ 7 days, maintain dose level -If resolved in > 7 days, decrease 1 dose level
Grade 3 (> 5.0– 20.0 x ULN) without total bilirubin elevation to > 2.0 x ULN	Omit dose until resolved to ≤ Grade 1, then decrease 1 dose level
Grade 4 (> 20.0 x ULN) without bilirubin elevation to > 2.0 x ULN	Permanently discontinue patient from eribulin
AST and/or ALT and Albumin	

Product: Grapiprant

Protocol 2021-0077 Proprietary Information of MD Anderson

DI. [name]

PI: [name] Co-PI: [name] Date: 11/22/2022

AST and/or ALT > ULN-3.0 x ULN (grade 2) and albumin < LLN - 3 g/dL (grade 1)	Omit dose until resolved to ≤ Grade 1, then -If resolved in ≤ 7 days, maintain dose level -If resolved in > 7 days, decrease 1 dose level				
AST and/or ALT > 3.0–5.0 x ULN and albumin < 3 - 2 g/dL (grade 2) without total bilirubin elevation to > 2.0 x ULN	Permanently discontinue patient from eribulin				
Bilirubin (*for patients with Gilbert Syndrome these dose modifications apply to changes in direct bilirubin only)					
Grade 1 (> ULN-1.5 x ULN)	Maintain dose level with LFTs** monitored per protocol				
Grade 2 (> 1.5–3.0 x ULN) with ALT or AST \leq 3.0 x ULN	Omit dose until resolved to \leq Grade 1, then: If resolved in \leq 7 days, then maintain dose level If resolved in $>$ 7 days, then decrease 1 dose level				
Grade 3 (> 3.0– 10.0 x ULN) with	Permanently discontinue patient from eribulin				

Dose Modifications for eribulin

ALT or AST $\leq 3.0 \text{ x ULN}$

*Hepatic toxicity monitoring for patients with Gilbert Syndrome: total and direct bilirubin must be monitored, intensified monitoring applies to changes in direct bilirubin only; the monitoring includes the following LFTs: albumin, ALT, AST, total bilirubin, alkaline phosphatase.

LFTs include albumin, ALT, AST, total bilirubin, alkaline phosphatase, and GGT

- Cycle 1 and 2: every other week (if visit schedule allows more frequent monitoring, this should be considered) or more frequently if clinically indicated, especially for patients with borderline acceptable AST/ ALT/ bilirubin* values
- Cycle 3 and onward: monthly or more frequently if clinically indicated

In case of any occurrence of ALT/AST/ bilirubin* increase \geq grade 2, LFTs must be monitored weekly or more frequently if clinically indicated until resolved to \leq grade 1.

In case of any occurrence of ALT/ AST/ bilirubin* increase \geq grade 3 LFTs must be monitored weekly or more frequently if clinically indicated until resolved to \leq grade 1; thereafter, the monitoring should be continued every other week or more frequently if clinically indicated. until the end of treatment with study medication

Patients who discontinued treatment with eribulin should be monitored weekly, including LFTs* or more frequently if clinically indicated until resolved to \leq grade 1 or stabilization (no CTCAE grade change over 4 weeks).

All other AEs	
Grade 1 or 2	Per physician discretion.
Grade 3	Omit dose until resolved to ≤ Grade 1, then decrease 1 dose level.
Grade 4	Permanently discontinue the patient from eribulin. Note: Omit dose for ≥ Grade 3 vomiting or Grade 3 nausea only if the vomiting or nausea cannot be controlled with optimal antiemetic treatment.

Protocol 2021-0077 Proprietary Information of MD Anderson PI: [name]

Co-PI: [name] Date: 11/22/2022

Dosing interruptions are permitted in the case of medical/surgical events or logistical reasons not related to study therapy (e.g., elective surgery, unrelated medical events, patient vacation, and/or holidays). Subjects should be placed back on study therapy within 3 weeks of the scheduled interruption. The reason for interruption should be documented in the patient's study record. Subjects who experience a recurrence of the same severe or life-threatening event at the same grade or greater with a re-challenge of grapiprant will be discontinued from trial treatment.

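### The Section 4.4.2 text resumes eribulin at grade 2 or less, several Table 3 rows hold it until grade 1, and nothing says which governs

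*Combined protocol and SAP*

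**What the plan says.** The eribulin text of Section 4.4.2 first lists when eribulin is not given on day 1 or day 8: grade 3 or higher neutropenia, grade 2 or higher thrombocytopenia, or "grade 3/4 nonhematologic toxicities". It lets the day 8 dose slip by up to a week for toxicity, and then sets the release rule: "If toxicities resolve or improve to grade 2 or less by day 15", eribulin is given at a reduced dose. The converse follows: "If toxicities do not resolve or improve to grade 2 or less by day 15, we will omit the dose". A further sentence is not tied to day 8: "If a dose has been delayed for toxicities that have recovered to the severity of grade 2 or less, resume the recommended reduced dose".

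Table 3, in the same section, works by toxicity and grade. For grade 3 AST/ALT (without the stated bilirubin rise), for the upper peripheral neuropathy row (printed as Grade > 3) and for grade 3 events under All other AEs, it says "Omit dose until resolved to ≤ Grade 1, then decrease 1 dose level". For grade 3-4 anemia it says "Hold eribulin until hemoglobin is Grade 1, then decrease 1 dose level". For grade 2 neuropathy it says "Omit dose until resolved to ≤ Grade 1, then restart at the same dose". Grade 2 AST/ALT or bilirubin keeps the same dose level if resolved within 7 days. Grade 4 events under All other AEs lead to permanent discontinuation of eribulin.

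Section 4.4.1 sends the reader to Table 3 for recommended modifications and re-initiation criteria. Section 4.4.2 calls Tables 2 and 3 a summary of those criteria. Neither section says which prevails if text and table differ.

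**The concern.** The text and the table appear to answer the same question, when eribulin may be given again after toxicity, with different grades. If so, an investigator cannot follow both, and two patients with the same course could be treated differently with each treatment being according to protocol.

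Eribulin is the backbone of the combination, so patient safety comes first. The restart rule also sets how much eribulin patients receive while clinical benefit is assessed in a 25-patient trial. The grade 4 mismatch has a further consequence. Under Section 4.4.2, a participant who must stop eribulin for an adverse event may stay on grapiprant only with demonstrated clinical benefit and the supporting company's agreement, so which passage is followed can decide who remains on study treatment.

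**Working it through.** The plan gives no figure to reproduce. The check sets the passages side by side, followed by a simple count.

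**Step 1. Test case.** Take a grade 3 non-hematologic event on day 8 that has improved to grade 2 on day 15. Under the text the dose was withheld, the toxicity is now grade 2 or less, and eribulin is given at a reduced dose. Under Table 3 the event has not reached grade 1, so the dose stays omitted. Section 4.4.2 also bases dose modifications on the worst preceding toxicity, so the patient cannot simply be moved to a grade 2 row on improvement. For AST/ALT that would not help in any case, because the grade 2 row also omits until grade 1 or less.

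**Step 2. Row by row, once the event has improved to grade 2.**

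| Toxicity | Text | Table 3 | Conflict on threshold |
|---|---|---|---|
| AST/ALT, grade 3 | Give, reduced | Hold to grade 1 or less | Yes |
| Neuropathy, upper row (printed Grade > 3) | Give, reduced | Hold to grade 1 or less | Yes |
| All other AEs, grade 3 | Give, reduced | Hold to grade 1 or less | Yes |
| Anemia, grade 3-4 | Give, reduced, if the dose was delayed | Hold to grade 1 | Yes |
| Neutropenia | Give, reduced | Hold to ANC of at least 1,000 | No |

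Anemia is not in the text's list of withholding triggers. It conflicts through the general sentences on delayed doses. Neutropenia agrees because the DLT definition in Section 4.4.2 puts grade 3 ANC at below 1,000 down to 500/mm³, so an ANC of at least 1,000 is grade 2 or less.

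**Step 3. Three further mismatches.**
- *Restart dose.* After a hold for grade 2 neuropathy, or for grade 2 AST/ALT or bilirubin resolved within 7 days, Table 3 keeps the dose unchanged. The text resumes delayed doses at a reduced dose and allows no re-escalation.
- *Grade 4 other events.* Table 3 discontinues eribulin permanently. The text groups grades 3 and 4 as triggers and lets the dose resume on recovery, without separating them.
- *Thrombocytopenia within the text.* The text withholds at grade 2 or higher and resumes at grade 2 or less. A patient at grade 2 meets both conditions.

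**Step 4. How many patients could reach these rows.** The inputs are the planned 25 patients and the eribulin column of Table 6 for grade 3 or higher: asthenia/fatigue 10%, peripheral neuropathy 8%.
- Asthenia/fatigue: 25 × 0.10 = 2.5 patients
- Neuropathy: 25 × 0.08 = 2 patients

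These are incidences at any time on eribulin, over a median exposure of 118 days (Section 6.2). The threshold conflict needs more: the event must be present when a dose is due and must stand at exactly grade 2 when re-dosing is decided. A patient still at grade 3, or already at grade 1 or less, gets the same give-or-hold answer from both passages. The documents do not give the share at grade 2 at that moment, so the figures are upper bounds. They may overlap in the same patients and should not be added. They leave out hepatic events.

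**The case against.** The best defence is that Table 3 is the specific rule and the text the general one, since Section 4.4.1 refers to the table for re-initiation. The trial is also run at a single center, whose investigators make all dose decisions (Section 4.12), so one reading may be applied throughout. Both points have some weight, but neither settles the matter. The referral calls the modifications recommended, the text states what will be done, and no precedence is given. Consistent practice at one center would not tell a later reader which rule was used.

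Several stronger readings are tempting and are not supported:

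- *Every Table 3 row conflicts.* It does not. Neutropenia, at 57% grade 3 or higher the most frequent severe toxicity in Table 6, agrees on the resume threshold. Grade 3 bilirubin (with ALT/AST up to 3 x ULN) is a permanent discontinuation, so no hold until grade 1 arises. Grade 3 nausea or vomiting is omitted only if antiemetics fail.
- *Table 3's holds for grade 2 neuropathy, AST/ALT or bilirubin contradict the text.* The text allows a day 8 delay for toxicity with no grade stated, so these holds can be read as additional. The restart dose is the clear mismatch.
- *A longer hold makes the patient unevaluable under Section 4.9.2.* The delay clause there concerns major protocol violations. A toxicity hold that the protocol itself directs is not clearly one.
- *The primary outcomes are biased.* DLTs are defined by events in cycle 1, not by the restart threshold, and nothing in the documents allows an effect on the clinical benefit rate to be sized.

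The upper neuropathy row is another limit. Read literally, Grade > 3 does not include grade 3, so the neuropathy count of 2 assumes that the row was meant to cover it.

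**Conclusion.** The contradiction is real and unreconciled, within limits. For grade 3 AST/ALT, the upper neuropathy row, grade 3 other events and grade 3-4 anemia, improvement to grade 2 brings a dose under the text and a hold under Table 3. The restart dose after some grade 2 events, the handling of grade 4 other events, and the text's own thrombocytopenia rule also need to be aligned.

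The size is at most about 2.5 of 25 patients through asthenia/fatigue and 2 of 25 through neuropathy. This assumes that the Table 6 rates for eribulin alone carry over to the combination and that the upper neuropathy row includes grade 3. A reader might infer that this many patients will receive conflicting instructions. The documents do not support that, because they do not say how many would be at grade 2 when re-dosing is decided. The case for correction rests on two incompatible dosing instructions in a safety matter, not on a demonstrated effect on either primary outcome.

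**What to change.** Reconcile the eribulin text of Section 4.4.2 with Table 3 so that each toxicity has one hold criterion, one resume criterion and one restart-dose rule, and state which passage governs if they differ. The same revision should settle how grade 4 other events are handled, whether the upper neuropathy row includes grade 3, and what applies to a patient at grade 2 thrombocytopenia. Which thresholds and doses are right is for the clinical investigators and the sponsor, and no view is taken here.

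The cost is protocol wording only. The sample size, the decision boundaries and the analyses do not change.
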